### 5. TABLE OF EVENTS

**Table 4: Table of Events**

Events Table covers both Phase 1b & 2 (unless otherwise noted)	Screening Period	Treatment Period a							Follow-up Period a	
	Screening  Days -28 to -1	28-day cycles							EOT b	Follow-up
		Cycles 1 to 2				Cycles 3 to 4		Cycle 5 and beyond		
		Day 1	Day 8	Day 15	Day 22	Day 1	Day 15	Day 1		
Informed Consent	× c	-	-	-	-	-	-	-	-	-
IWRS Subject Status Registration (Phase 1b/2)	×	× d	-	-	-	×	-	×	×	-
Inclusion & Exclusion Criteria	×	× e,f	-	-	-	-	-	-	-	-
Demographics	×	-	-	-	-	-	-	-	-	-
AML Diagnosis	× g	-	-	-	-	-	-	-	-	-
Local Testing of IDH1/ IDH2 Gene Mutations on BMA and PB (In addition, BMA and PB samples to be sent to central lab)	× g	-	-	-	-	-	-	-	-	-
Medical History	×	-	-	-	-	-	-	-	-	-
Prior Medications and Procedures	× h	-	-	-	-	-	-	-	-	-
EORTC QLQ-C30 and EQ-ED-5L	-	×	-	-	-	×	-	×	×	-
ECOG Performance Status	×	×	-	-	-	×	-	×	×	-
Physical Examination i	×	×	-	-	-	×	-	×	×	-
Vital Signs	×	×	×	×	×	×	×	×	×	-

**Table 4: Table of Events (Continued)**

Events Table covers both Phase 1b & 2 (unless otherwise noted)	Screening Period	Treatment Period a								Follow-up Period a
	Screening	28-day cycles							EOT b	Follow-up
		Cycles 1 to 2				Cycles 3 to 4		Cycle 5 and beyond		
		Days -28 to -1	Day 1	Day 8	Day 15	Day 22	Day 1	Day 15		
ECHO / MUGA Scan k	× l	As clinically indicated								-
Height	×	-	-	-	-	-	-	-	-	-
Body Weight	×	×	-	-	-	×	-	×	×	-
BSA Calculation j	×	×	-	-	-	×	-	×	-	-
12-Lead ECG k	×	×	-	×	-	×	-	×	×	-
Pregnancy Test (FCBP only) m	× n	× k,o	-	-	-	× k	-	× k	× k	-
Urinalysis n	×	As clinically indicated								-
Coagulation Laboratory n	×	As clinically indicated								-
Hematology Laboratory n	×	×	×	×	×	×	×	×	×	× p
Chemistry Laboratory n	×	×	-	×	-	×	-	×	×	-
UGT1A1 Gene Mutation Test (for diagnosis of Gilbert's Syndrome; refer to Section 4.2) n	×	-	-	-	-	-	-	-	-	-
Cardiac Markers n	-	× f	× q						-	
Fasting Lipid Panel n	-	× f	× r						-	
Adverse Event	× s									

**Table 4: Table of Events (Continued)**

Events Table covers both Phase 1b & 2 (unless otherwise noted)	Screening Period	Treatment Period a							Follow-up Period a	
	Screening	28-day cycles							EOT b	Follow-up
		Cycles 1 to 2				Cycles 3 to 4		Cycle 5 and beyond		
		Days -28 to -1	Day 1	Day 8	Day 15	Day 22	Day 1	Day 15		
Concomitant Medications and Procedures	Continuous until 28 days after the last study treatment									
Transfusion Data Collection and Assessment†	Assess and record on an ongoing basis (prior to each dose of IP) until the next AML therapy after discontinuation from study treatment, death, lost to follow-up, withdrawal of consent for further data collection, or the End of Trial, whichever occurs first. Clinical site staff should confirm if any transfusions were received by the subject (including any at outside local institutions in between study visits) prior to each IP administration via use of patient diary or other local procedure in place at the investigational site.									
BMA for Disease Assessmentv, g	x	x w	-	-	-	x x	-	x y	x z	x p
Blood for Pharmacodynamicsg, v	x	x	-	x	-	x x	-	x y	x z	x p
BMBg, bb	x	x w	-	-	-	x x	-	x y	x z	x p
PB Smearg	x	x w	-	-	-	x x	-	x y	x z	x p
Cytogenetics Testingg	x	x w, cc	-	-	-	x x, cc	-	x y, cc	x z, cc	x p, cc
Modified IWG Response and HI	-	x w	-	-	-	x x	-	x y	x z	x p

**Table 4: Table of Events (Continued)**

Events Table covers both Phase 1b & 2 (unless otherwise noted)	Screening Period	Treatment Period a							Follow-up Period a	
	Screening	28-day cycles							EOT b	Follow-up
		Cycles 1 to 2				Cycles 3 to 4		Cycle 5 and beyond		
		Days -28 to -1	Day 1	Day 8	Day 15	Day 22	Day 1	Day 15		
PB for Pharmacokinetics (AG-120 only in Phase 1b / AG-221 only in Phase 2)	-	× ee	-	-	-	× ee	-	-	-	-
IP Accountabilitydd	-	× ff	-	-	-	×	-	×	×	-
AG-120 / AG-221 Dispensation	-	×	-	-	-	×	-	×		-
Azacitidine Treatment Administration	-	See Section 7.2 for details							-	-
Survival Follow-up	-	-	-	-	-	-	-	-	-	× gg
Subsequent AML Therapies	-	-	-	-	-	-	-	-	-	× gg

Abbreviations: AML = acute myeloid leukemia; β-hCG = β-subunit of human chorionic gonadotropin; BMA = bone marrow aspirate; BMB = bone marrow biopsy; BSA = body surface area; CR = morphologic complete remission; ██████████ ECHO = echocardiogram; eCRF = electronic case report form; ECG = electrocardiogram; ECOG = Eastern Cooperative Oncology Group; EORTC = European Organization for Research and Treatment of Cancer; FCBP = female of childbearing potential; EOT = End of Treatment; HI = hematologic improvement; HSCT = hematopoietic stem cell transplantation; ICF = informed consent form; IDH2 = isocitrate dehydrogenase isoform 2; IP = investigational product; IWG = International Working Group; IWRS = interactive web response system; ██████████ MUGA = multi-gated acquisition; PK = pharmacokinetics; PB = peripheral blood; ██████████ SOC = standard of care; UGT1A1 = uridine diphosphate-glucuronosyltransferase 1 family, polypeptide A1

a One cycle (one month) is considered as 28 days (ie, 4 weeks). Unless noted otherwise, an administrative window of ± 3 days is permitted for all subsequent visits after the start of study treatment in each treatment cycle in the Treatment Phase. Day 1 of Cycles 2 and beyond may be delayed from Day 28 of the prior cycle in order for subjects to recover from toxicity and meet criteria for initiating each treatment cycle (Section 7.2). The study visit window for EOT or monthly-scheduled survival follow-up is ± 7 days.

b See Section 6.2.3 for details.

c Including informed consent for mandatory genetic testing ██████████.

d The subject should start study treatment (ie, Day 1 of Cycle 1) within 3 days after enrollment or randomization.

e Subject should continue to be eligible for study entry prior to the start of study treatment on Day 1 of Cycle 1.

f Cycle 1 only.

g See Section 6.1 for details regarding collecting BMA, BMB, PBS, and cytogenetics at screening for assessing AML diagnosis, collecting BMA and PB at screening for potential retrospective confirmation of mutational status, and collecting BMA and PB at screening for pharmacodynamics ██████████.

[figure not shown]

[figure not shown]
- h All prior medications (prescription and non-prescription) taken and treatment procedures received from the 4-week period (ie, 28 days) prior to starting study treatment (including those prior to the start of study treatment on Day 1 of Cycle 1) and all prior anticancer therapies, regardless of discontinuation date of treatment.
- i Source documented only.
- j The BSA calculation is per the Dubois & Dubois formula:  $BSA (m^2) = \text{weight (kg)}^{0.425} \times \text{height (cm)}^{0.725} / 139.2$ . The dose should be calculated on Day 1 of each treatment cycle. The dose during a treatment cycle should not be amended.
- k These assessments will be done locally. See Section 6.2 for details.
- l If an assessment has been performed within 28 days prior to the start of study treatment, it does not need to be repeated.
- m Pregnancy test is required for all FCBPs (see Section 4.2 for the definition). Serum  $\beta$ -hCG pregnancy test (sensitivity of at least 25 mIU/mL) will be performed centrally at screening. For FCBP subjects, a local serum  $\beta$ -hCG pregnancy test (sensitivity of at least 25 mIU/mL) is to be done within 72 hours prior to study treatment administration on Day 1 of every treatment cycle in the Treatment Phase and at the EOT Visit. Negative results are required for study treatment administration.
- n These assessments will be done centrally. See Section 6.2 for details.
- o A local serum pregnancy test (sensitivity of at least 25 mIU/mL) is to be done within 72 hours prior to the start of study treatment in the Treatment Phase for FCBP only (note that the screening central serum pregnancy test can be used as the test prior to the start of study treatment in the Treatment Phase if it is performed within the 72-hour timeframe).
- p Whenever response/diagnosis is assessed in the Follow-up Period (ie, every 8 weeks [ $\pm$  28 days]). See Section 6.3 for details.
- q Day 1 ( $\pm$  14 days) of every 3rd cycle (eg, Cycles 3, 6, 9, etc) or more frequently per standard institutional practice. Not necessary for the EOT Visit if last performed within 14 days.
- r Day 1 ( $\pm$  28 days) of every 6th cycle (eg, Cycles 6, 12, 18, etc) or more frequently per standard institutional practice. Not necessary for the EOT Visit if last performed within 28 days.
- s Continuous starting after signing ICF through 28 days after the last study treatment. See Section 6.4.1 for details.
- t Including type, number of units, reasons, and date of transfusions taken  $\leq$  8 weeks prior to the start of study treatment through 28 days after the last study treatment. Thereafter, transfusions will continue to be collected until the next AML therapy after discontinuation from study treatment, death, lost to follow-up, withdrawal of consent for further data collection, or the End of Trial, whichever occurs first.
- v In addition to the frequency specified in the table, samples will also be collected if clinically indicated (eg, confirmation of CR/CRi/CRp, morphologic relapse after CR/CRi/CRp, or progression by a repeated bone marrow assessment at least 1 month later) or required for toxicity assessment. A sample of bone marrow and peripheral blood must also be sent at these time points for central pathology review.
- w Within 7 days prior to Day 1 of Cycle 2. The assessment is not required at Day 1 of Cycle 1.
- x Within 7 days prior to Day 1 of Cycle 3. The assessment is not required at Day 1 of Cycle 4.
- y Within 7 days prior to Day 1 of Cycle 5 and Day 1 of every 2nd cycle thereafter (eg, Cycles 7, 9, etc).
- z Not necessary for the EOT Visit if last performed within 28 days.
- bb A bone marrow biopsy can be collected in conjunction with an aspirate if it is standard institutional practice. A bone marrow biopsy must be collected if adequate aspirate is not attainable.
- cc A standard cytogenetic metaPhase preparation will be prepared if the bone marrow aspirate is obtained for assessing CR, morphologic relapse, or progressive disease and will be sent to the local laboratory for cytogenetic analysis.
- dd Including diary cards. See Section 7.6 for details.
- ee Intensive PK sampling is performed as defined in Table 6 for AG-120 subjects in the Phase 1b Expansion on all subjects, and Table 7 in Phase 2 for AG-221 subjects at select sites for the first 6 - 12 subjects. Sparse PK sampling will be performed on all other AG-221 subjects at the selected sites as well as all other sites as defined in Table 8.

ff Cycle 2 only.

gg Every 4 weeks ( $\pm$  7 days) for survival follow-up until death, lost to follow-up, withdrawal of consent for further data collection or the End of Trial, whichever occurs first.  
Subsequent AML therapies should be collected at the same time schedule. See Section 6.3 for details.

■ [REDACTED]

**Table 6: AG-120 Intensive Pharmacokinetic Sampling in Phase 1b Expansion**

Visit/Cycle:	Cycle 1	Cycle 1	Cycle 2
Study Day:	D1	D15	D1
Pre-dose a	X	X	X
Post-dose			
0.5 hr b	X	-	X
2 hr b	X	-	X
3 hr b	X	-	X
4 hr b	X	-	X
6 hr b	X	-	X
8 hr b	X	-	X

a Within 30 minutes prior to AG-120

b ± 10 minutes

Note: Intensive pharmacokinetic sampling for AG-120 will be conducted during the Phase 1b expansion.

**Table 7: AG-221 Intensive Pharmacokinetic Sampling in Phase 2**

Visit/Cycle:	Cycle 2	Cycle 3
Study Day:	D1	D1
Pre-dose a	X	X
Post-dose		
2.0 hr b	X	-
3.0 hr b	X	-
4.0 hr b	X	-
6.0 hr b	X	-
8.0 hr b	X	-
24.0 hr b	X	-

a Within 30 minutes prior to AG-221

b ± 10 minutes

Note: Intensive pharmacokinetic sampling for AG-221 will be conducted at selected sites during Phase 2

**Table 8: AG-221 Sparse Pharmacokinetic Sampling in Phase 2**

	Cycle 2	Cycle 3
	D1	D1
Pre-dose a	X	X
Post-dose		
4.0 hr a	X	-

a Within 30 minutes prior to AG-221

b ± 10 minutes

Note: Sparse pharmacokinetic (PK) sampling for AG-221 will be conducted at all sites during Phase 2. Subjects who participate in the intensive PK will not have additional samples collected.

## 6. PROCEDURES

Any questions regarding the protocol should be directed to the medical monitor or designee.

Signed ICFs must be obtained before any study evaluations are performed and any samples are collected per local regulations during the course of the study.

### 6.1. Screening period

Screening evaluations must be completed within 28 days prior to the start of study treatment, unless noted otherwise below. Screening laboratory values must demonstrate subject eligibility, but may be repeated once within the screening window, if necessary.

The following will be performed at screening as specified in the Table of Events (Table 4) after written ICF has been signed:

- Registration of screening in interactive web response system IWRS
- Inclusion and exclusion criteria
- Demographics (age, sex, race, and ethnicity)
- Gather information supporting the initial diagnosis of AML by local pathology and cytogenetics, including reports of bone marrow aspirate and/or biopsy, peripheral blood smear, cytogenetics, and other tests if pertinent
- AML diagnosis at screening will be determined by local pathology and cytogenetics review. The pathology will be confirmed retrospectively by a central pathology review. Therefore, bone marrow aspirate (or biopsy if adequate aspirate is not attainable) must be collected at screening such that slides of bone marrow aspirate (and/or biopsy) and peripheral blood smears are available for both the local and the central pathology reviews. A bone marrow biopsy can be collected in conjunction with an aspirate if it is standard institutional practice. Whenever a bone marrow sample is collected, a peripheral blood smear is to be prepared. In addition, a standard cytogenetic metaPhase preparation will be prepared from the screening bone marrow aspirate and sent to the local laboratory for cytogenetic analysis.

The retrospective central pathology review will require a set of duplicate slides for each bone marrow collection time point including bone marrow aspirate (BMA), peripheral blood smear, and bone marrow biopsy (BMB) if performed. The central pathology review will be conducted by personnel blinded to study treatment. The central assessments will be used to confirm AML diagnosis at screening. If the subject was centrally confirmed to not be a candidate for the study, the subject will be replaced for analysis purposes but allowed to remain in the study, and will be excluded from the modified intent-to-treat (mITT) population (Section 9).

Instructions for submitting slides of bone marrow aspirate (and/or biopsy) and peripheral blood smear for central pathology review are provided in the Study Reference and/or Study Central Laboratory Manual.

- IDH mutational status will be assessed locally; for sites without local testing capabilities, a referral lab will be identified. A bone marrow aspirate and peripheral

blood sample must be sent [REDACTED] to the central lab for potential retrospective confirmation of mutational status.

[figure not shown]
Refer to the Study Reference and/or Study Laboratory Manual for sample collection, processing, storage, and shipment procedures.

- Medical history including all relevant current medical conditions and medical conditions diagnosed/ occurring prior to screening
- Prior medications including those taken  $\leq 28$  days prior to the start of study treatment
- Prior procedures including those occurring  $\leq 28$  days prior to the start of study treatment
- ECOG performance status
- Physical examination: information about the screening physical examination must be present in the subject's source documentation. Significant findings must be included on the appropriate eCRF page.
- Vital signs including temperature, blood pressure, pulse rate and respiratory rate
- Body weight
- Height
- Body surface area (BSA) calculation per the Dubois & Dubois formula:  
 $BSA (m^2) = \text{weight (kg)}^{0.425} \times \text{height (cm)}^{0.725} / 139.2$
- The following laboratory assessments will be done locally:
  - ECHO or MUGA scan (not required if an assessment has been performed within 28 days prior to the start of study treatment)
  - 12-lead ECG will be assessed by a physician trained in ECG interpretation as normal, abnormal - not clinically significant, or abnormal - clinically significant. Intervals including PR, QRS, QT, and RR will be collected, as well as heart rate and rhythm. Abnormal clinically significant finding(s) will be reported on the appropriate eCRF page. For a given subject, ECG interpretations should be conducted by the same physician throughout the study as much as possible, with a consistent approach for the QT interval analysis (eg, pre-cordial leads and lead II).
- The following laboratory assessments will be done centrally:
  - Serum  $\beta$ -hCG pregnancy test (sensitivity of at least 25 mIU/mL) is required for all FCBPs (see Section 4.2 for the definition)
  - Urinalysis including examination by a standard dipstick test for specific gravity, glucose, ketones, blood, pH, and protein, and microscopic analysis if indicated
  - Coagulation test including prothrombin time (PT) with international normalized ratio (INR) and partial thromboplastin time (PTT)
  - Hematology panel including complete blood count (CBC) with differential, including red blood cell (RBC) count, hemoglobin, hematocrit, mean corpuscular

volume (MCV), mean corpuscular hemoglobin (MCH), mean corpuscular hemoglobin concentration (MCHC), WBC count (with differential), absolute neutrophil count (ANC), and platelet count

- Chemistry panel including sodium, potassium, calcium, magnesium, chloride, phosphorus, CO2, bicarbonate, blood urea nitrogen (BUN), creatinine, glucose, albumin, total protein, alkaline phosphatase, bilirubin (total and direct), uric acid, lactate dehydrogenase (LDH), AST/SGOT, ALT/SGPT, amylase, and lipase
- UGT1A1 gene mutation test performed on peripheral blood samples for diagnosis of Gilbert's syndrome (refer to the inclusion criterion regarding serum total bilirubin in Section 4.2)
- Assessing AEs [REDACTED] start when the subject signs the ICF
- Transfusion history including the type, number of units, reason, and date of transfusions for the 8 weeks prior to the start of study treatment
- At screening, bone marrow aspirate sampling for pharmacodynamic assessments will be performed in subjects of all treatment arms if sufficient bone marrow material remains after bone marrow aspirate sampling for assessing AML diagnosis and testing IDH1 / IDH2 gene mutation status. Refer to the Study Reference and/or Study Laboratory Manual for sample collection, processing, storage, and shipment procedures.

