## **9.3. Sample Size and Power Considerations**

The Phase 1b dose-finding stages will enroll a total of approximately 24 subjects. Additional subjects may be enrolled in a dose level to replace subjects who are not evaluable for the primary endpoint, or for further exploring safety, PK, PK/pharmacodynamic, or preliminary clinical activity.

In Phase 1b AG-120 expansion stage, to ensure acceptable toxicity at the RCD, up to 15 subjects will be accrued into the AG-120 expansion phase. Based on a sample size of 18 AML subjects treated at RCD (ie, 15 subjects in the dose expansion and around 3 subjects in the dose escalation), there is 95% probability of detecting 1 or more AEs with an underlying rate of 15%, and 85% probability of detecting 1 or more AEs with an underlying rate of 10%.

In Phase 2 AG-221 randomized stage, subjects with AML with IDH2 mutation will be randomized to receive oral AG-221 + SC azacitidine versus SC azacitidine in a 2:1 ratio. A minimum of 99 subjects will be randomized in this phase with 66 subjects in the oral AG-221 + SC azacitidine arm, and 33 subjects in the SC azacitidine mono therapy arm. The statistical comparisons will be conducted for oral AG-221 + SC azacitidine versus azacitidine mono

therapy. Assuming an overall response rate (ORR) of 30% in the azacitidine mono therapy and an ORR of 50% for oral AG-221+ SC azacitidine arm, the sample size of 66 subjects in AG-221 + SC azacitidine arm and 33 patients in SC azacitidine mono therapy arm will provide 75% power to detect a 20% difference in ORR at a two-sided type I error rate of 0.2. The multiple comparison was not considered in the sample size calculation.

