### 3. Change of the stratification factor from cytogenetic risk to primary (ie, de novo) or secondary (progression of MDS or myeloproliferative neoplasms [MPN], or therapy-related) AML

Sample processing requirements along with result times of up to 2 weeks at some centers in this newly diagnosed AML population could negatively impact a subject's ability to enter into this study due to the need to initiate treatment prior to receiving cytogenetic results. For this Phase 1b/2 study, stratification will now be de novo versus secondary AML to limit potential bias related to poorer prognosis and treatment resistance in the secondary AML population.

Revised Sections: Protocol Summary, 3.1.2, 7.2.2.2, 7.3

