4.3. Stratification, Randomization, and Blinding

Randomization only applies to the Phase 2 part and will be carried out using an Interactive Web Response System (IWRS). Subjects with an IDH2 mutation will be randomized to receive oral AG-221 + SC azacitidine (Arm 1) versus SC azacitidine (Arm 2) in 2:1 ratio. Arm 1 will include a minimum of 66 subjects and Arm 2 will include a minimum of 33 subjects, (99 subjects total in both arms).

For the Phase 2 part, all subjects randomized will be stratified by primary (i.e., de novo) or secondary (progression of MDS or myeloproliferative neoplasms [MPN], or therapy-related) AML according to the WHO classification.

During Phase 1b and Phase 2 a retrospective central pathology review of all bone marrow aspirates and/or biopsies and peripheral blood smears, which are collected in subjects of the AG-221 (Phase 1b dose-finding and Phase 2 randomized stage) treatment arms during screening, will be conducted by personnel blinded to subject treatment to confirm eligibility. Bone marrow aspirate and/or biopsy and peripheral blood smear collected after the start of study treatment must be available for both local and central pathology review. The retrospective central pathology review will require a set of duplicate slides for each bone marrow collection time point including bone marrow aspirate (BMA), peripheral blood smear, and bone marrow biopsy (BMB) if performed. The central pathology review will be conducted by personnel blinded to study treatment.

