10.2.1. Event-free survival

EFS is assessed by investigator based on modified International Working Group (IWG) AML response criteria (Section 17.4).

Event-free survival (EFS) is defined as the interval from either the date of the first dose for subjects in Phase 1b or the date of randomization for subjects in Phase 2 to the date of documented morphologic relapse, progression, or death from any cause, whichever occurs first. Censoring rules are provided in Table 4. The analysis of the EFS for Phase 2 will be conducted using the log-rank test in the ITT population, and mITT population. The Cox proportional hazards regression model will be used to estimate the hazard ratio and the corresponding 95% confidence interval for oral AG-221 with SC azacitidine relative to SC azacitidine alone.

Additionally, the number of events, the number of censored and reasons for censoring will be summarized (n, percent) for this endpoint. KM curves will be provided by treatment arm in figures.

Table 4: Censoring Rules for EFS

Value of Event-free Survival Date (ADT)	Censored (Y, N)	Derivation
ADT = min(death date, MR date, progression date)	N	If a subject died, had MR, or had disease progression by investigator review, and the subject has less than two consecutive missing response assessments prior to a visit documented death, MR, or progression which is before new AML therapy
ADT = the last event-free assessment date before missing assessments/ randomization date	Y	If a subject died, had MR, or had disease progression by investigator review, and the subject has two or more consecutive missing response assessments prior to a visit documented death, MR, or progression
ADT = the last adequate assessment date/randomization date	Y	If a subject did not die, did not have MR, or did not have progression, and did not receive any subsequent anticancer therapy. If there was no post-baseline response assessment, then ADT = the randomization date.
ADT = the last adequate assessment date on or prior to start of subsequent anticancer therapy/randomization date	Y	If a subject did not die, did not have MR, or did not have progression on or prior to start of subsequent anticancer therapy. If there was no post-baseline response assessment, then ADT = the randomization date.

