10.2.4. Overall Survival

Overall survival (OS) is defined as time from first date of study drug (Phase 1b) or randomization (Phase 2) to death due to any cause. This time to event endpoint will be analyzed, similarly to the EFS analyses described in 10.2.1. Sensitivity analysis for OS may be explored if needed.

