10.3. Subgroup Analysis

Appropriate subgroup analyses will be conducted for primary and selected secondary efficacy endpoints by the following subgroups for Phase 2:

1. Age groups (< 65 years, ≥ 65 to < 75 years, ≥ 75 years);
2. Gender (male and female);
3. Region (US, Non-US);
4. Race (white vs non-white);
5. Baseline cytogenetic risk status (better-risk, intermediate-risk, poor-risk, failure);
6. For IDH2 mutated subjects, IDH2 gene mutation sub-type (R140Q vs. R172K);
7. AML initial diagnosis: (primary or secondary);
8. WHO classification of AML;
9. ECOG performance status at baseline (Grade 0, 1, 2);
10. European LeukemiaNet (ELN) risk classification (favorable, intermediate and adverse).

A forest plot will be provided displaying the hazard ratios (for time to event endpoints) and odds ratios (for ORR) and their 95% CIs, obtained from Cox proportional hazards and logistic regression models, respectively, for each subgroup.

Subgroup analyses will be conducted for the following efficacy endpoints:

- Overall Response Rate;
- Overall Survival.

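### Cytogenetic risk is collected at baseline but left out of the EFS and OS Cox models, so a chance imbalance between arms would stay in the reported hazard ratios

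*Protocol*

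**What the plan says.** **Collection.** Protocol 6.1 (Screening period) states that "a standard cytogenetic metaPhase preparation will be prepared from the screening bone marrow aspirate and sent to the local laboratory for cytogenetic analysis". Appendix C defines better, intermediate and poor risk. SAP 8.2.1 tabulates cytogenetic risk status at baseline, with a failure level and with both local and central results.

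**Randomisation.** SAP 4.3 states that "all subjects randomized will be stratified by primary (i.e., de novo) or secondary (progression of MDS or myeloproliferative neoplasms [MPN], or therapy-related) AML". No other factor is named. The amendment log explains why cytogenetic risk is not a stratum: "Sample processing requirements along with result times of up to 2 weeks at some centers in this newly diagnosed AML population" could keep subjects who need to start treatment out of the study.

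**Analysis.** SAP 10.1 tests ORR with an unstratified chi-squared or Fisher test. For EFS, SAP 10.2.1 specifies a log-rank test and adds: "The Cox proportional hazards regression model will be used to estimate the hazard ratio and the corresponding 95% confidence interval for oral AG-221" with azacitidine relative to azacitidine alone. It names no strata or covariates. For OS, SAP 10.2.4 says "This time to event endpoint will be analyzed, similarly to the EFS analyses described in 10.2.1". SAP 10.2 takes the time-to-event p-value from the log-rank test. The three named EFS sensitivity analyses change only censoring and event rules.

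**Subgroups.** SAP 10.3 lists "Baseline cytogenetic risk status (better-risk, intermediate-risk, poor-risk, failure" among ten factors, but the endpoints covered are ORR and OS only.

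**The concern.** Slow turnaround is a sound reason not to stratify on cytogenetics. It is no reason to leave them out of the analysis, because the sample is taken at screening and the result is known long before database lock. The protocol itself grades this factor by prognosis. As planned, a chance excess of poor-risk subjects in one arm passes straight into the EFS and OS hazard ratios. The baseline table would show the imbalance, but no prespecified estimate would account for it. A subgroup forest plot does not give an adjusted overall effect, and EFS, the first-listed secondary endpoint, does not get even that. In an open-label trial, choosing covariates after seeing the imbalance would carry little weight.

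**Working it through.** **1. The plan's own figure.** Inputs from Protocol 9.3: "Assuming an overall response rate (ORR) of 30% in the azacitidine mono therapy and an ORR of 50% for oral AG-221+ SC azacitidine arm", with 66 and 33 subjects, which "will provide 75% power to detect a 20% difference in ORR at a two-sided type I error rate of 0.2".
- Pooled rate = (33 × 0.30 + 66 × 0.50)/99 = 0.433.
- SE under the null = sqrt(0.433 × 0.567 × (1/33 + 1/66)) = 0.1057.
- SE under the alternative = sqrt(0.21/33 + 0.25/66) = 0.1008.
- Power = Φ((0.20 − 1.2816 × 0.1057)/0.1008) = Φ(0.641) = 73.9%.
- Exact enumeration of the uncorrected chi-squared test gives 75.3%, so the stated 75% is reproduced.

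**2. How often the arms differ.** The documents give no poor-risk share, so p is assumed. SD of the arm difference = sqrt(p(1 − p)(1/66 + 1/33)), with a normal approximation.

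| Poor-risk share (assumed) | SD | Chance of a gap of 10 points or more |
|---|---|---|
| 15% | 0.076 | 19% |
| 25% | 0.092 | 28% |
| 35% | 0.102 | 33% |
| 40% | 0.104 | 34% |

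**3. What a gap does to the hazard ratio.** The documents give no prognostic hazard ratio either. Simulation assumptions: treatment hazard ratio 0.60; exponential event times; control median 10 months in non-poor risk; uniform censoring at 12 to 36 months; (share, prognostic hazard ratio) = (25%, 2.0), (35%, 2.0), (35%, 2.5).
- Averaged over all allocations: unadjusted 0.61 to 0.63, adjusted 0.59 to 0.60.
- Combination arm has at least 10 points more poor risk (13% to 17% of trials): unadjusted 0.68 to 0.73, adjusted 0.59 to 0.61.
- The opposite gap (15% to 17% of trials): unadjusted 0.55 to 0.56, adjusted 0.59 to 0.60.

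A hand check agrees. Given a gap of at least 10 points in one direction, its mean is SD × φ(z)/(1 − Φ(z)) with z = 0.10/SD. That is 14.7 points at a 25% share and 15.4 points at 35%. To first order the hazard ratio is multiplied by exp(ln(prognostic HR) × gap):
- exp(0.693 × 0.147) = 1.107, and 0.61 × 1.107 = 0.68.
- exp(0.916 × 0.154) = 1.151, and 0.63 × 1.151 = 0.73.
- In the other direction, 0.61/1.107 = 0.55 and 0.63/1.151 = 0.55.

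**4. Average power for EFS and OS (two-sided 0.05).** A separate simulation compared unstratified with cytogenetic-stratified log-rank tests. It assumed a treatment hazard ratio of 0.55 to 0.60, a poor-risk share of 30% or 40%, and about 58 to 69 events.

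| Prognostic HR (assumed) | Unstratified | Stratified |
|---|---|---|
| 1.5 | 60% / 50% | 60% / 49% |
| 2 | 59% / 49% | 62% / 51% |
| 3 | 55% / 44% | 64% / 53% |

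In the setting of step 3, testing with the adjusted Cox model gives 56% / 54% / 56% against 52% / 50% / 48% unadjusted. At a prognostic hazard ratio of 1.5 the gain there is under 1 point (54.0% to 54.2% and 54.1% to 54.8%).

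**5. The primary ORR test.** With an assumed poor-risk share of 30% to 40% and prognostic odds ratio of 1.5 to 4, adjustment changes average power by −1 to +2 points. Unadjusted power stays near 75% and type I error near 0.20. If poor risk lowers ORR by 20 points, a 1-SD imbalance shifts the ORR difference by about 0.20 × 10 = 2 points.

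**The case against.** The strongest case against runs as follows.

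- **The omission is partly deliberate and partly handled.** The stratum was dropped for a stated practical reason, its replacement was chosen with prognosis in mind, the baseline table will expose an imbalance, and ORR and OS have cytogenetic and ELN-risk subgroups. This stands, but none of it yields an adjusted overall effect or covers EFS.
- **The average effect is small against the noise.** The mean hazard ratio moves by 0.02 to 0.03, while the standard error of its log is about 0.25 (95% CI about 0.37 to 0.98 around 0.60). Part of that movement is non-collapsibility: the unadjusted hazard ratio validly answers a marginal question. This stands for the average, but not for the allocations in step 3.
- **The covariate is a choice.** Age, ECOG status, ELN risk and AML type are also in SAP 10.3, and the documents do not rank cytogenetic risk above them. This stands in part. Cytogenetic risk was at one time the planned stratum, and the randomisation factor should be in the model too.
- **The measure is imperfect.** Local and central results have no order of precedence, Appendix C includes molecular markers, and subjects already in a first azacitidine cycle may be screened. These are matters for the model specification.

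A reader might infer that the planned tests are biased, that type I error is inflated, or that the primary ORR test loses power. The documents and the calculations support none of these: randomisation makes the imbalance zero on average, and the ORR effect is negligible. Nor would a covariate in the Cox model raise the power of EFS and OS testing, because the p-value comes from the log-rank test.

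**Conclusion.** The point holds as a gap in estimation for EFS and OS. Under the assumed shares, roughly one trial in five to one in three would have a gap of 10 points or more in poor-risk share. With a prognostic hazard ratio of 2.0 to 2.5, the unadjusted hazard ratio would then average about 0.7 or about 0.55 when the truth is 0.60, with no prespecified estimate to set beside it. The error is conditional on the allocation and can go either way. The average power cost depends on a prognostic strength that the documents do not give: about 0 points at 1.5, a few at 2.0, and up to 9 or 10 at 3. The endpoints concerned are secondary, so this calls for a supportive analysis and no change to the design.

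**What to change.** In SAP 10.2.1 and 10.2.4, prespecify a supportive Cox model for EFS and OS. Include local baseline cytogenetic risk (better or intermediate; poor; failure or missing as its own level) and the randomisation factor, primary versus secondary AML. State that local results are used, since SAP 8.2.1 lists both sources. Report the adjusted hazard ratio with its 95% CI beside the planned unadjusted one. Keep the chi-squared and log-rank tests as they are, and make no claim that their power rises. An ORR difference standardised over the same levels is optional and supportive only.

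The latest protocol amendment says the primary-analysis study report was final as of 15 December 2020. A model added after that analysis must be labelled post hoc.

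The cost is SAP wording and one extra model per endpoint, with no new data or subjects. The downsides are that local karyotyping varies, some subjects will fall in the failure level, and the adjusted hazard ratio is a conditional estimate that differs slightly from the marginal one.
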